Study Visits Schedule: All visits will be performed in the Clinical Research Center (CRC) at the Phoenix VA. Completion of the entire study will involve up 3-4 visits to the CRC. After initial visit for obtaining of informed consent and screening, qualified patients will undergo a baseline testing (on the same day as screening visit or on a separate day), including blood collection for baseline measurements, and will be randomized to treatment (Lysulin™ or matching placebo). Study medication will be dispensed to the subject in a double-blinded fashion by Phoenix VA research pharmacist. Subjects will be instructed to take two tablets orally with breakfast, lunch and dinner. They will return to the CRC for clinical evaluation and blood draws after 6 and 12 weeks (final visit). Subjects will be instructed to not make major lifestyle modifications, including changes to their diet or exercise, during their study participation. At least one phone call contact will take place between interim visits to ensure medication is being taken appropriately and to help address any study related questions. At each visit a comprehensive assessment of side effects, medication compliance/competency and concurrent medical history will be obtained and entered into the database. Additional brief visits may occur as needed to ensure participant comfort/competency with treatment.

Study endpoints:

Primary: Fasting plasma glucose and HbA1c concentrations

Secondary: Fasting plasma AGEs, C-peptide concentrations and lipid measurements

Recruitment Approach: Participants will be recruited utilizing VA electronic medical records to identify potential candidates meeting inclusion criteria, as well as from the Phoenix VA primary care, specialty and women's clinics, community diabetes clinics, ads in VA newsletters and flyers,

permission to be contacted forms, on hold message, social media, clinic list, BISL, list of A1c results from lab, and through VINCI.

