Diabetes care during the study: The research team will provide diet and exercise guidance at baseline and review at subsequent study visits, and monitor side effects, medication changes or general health issues of all subjects. We will notify relevant PCP providers of study activity to avoid unnecessary diabetes medication changes during the study. Addition of diabetes agents will be discouraged, but of course supported if clinically indicated. However, general and diabetes healthcare and routine lab tests will be conducted by the PCP as warranted. With hypoglycemia, excessive hyperglycemia or other adverse events - we will work with the participant and/or primary care team to evaluate/change contributory diet or behavior and/or reduce/modify other diabetes medications as appropriate.

Biochemical analyses: Plasma glucose, HbA1c, creatinine and all safety screening will be measured at the VAMC clinical laboratory using established automated methods. Plasma C-peptide levels will be measured by commercial ELISA kit in the VAMC research laboratory. AGEs will be measured by LC-MS/MS utilizing internal stable heavy isotope substituted standards (Preventage Healthcare technology) if initial data analysis indicates Lysulin had a rapid and favorable effect on HbA1c values.

Data Handling: All participants will be given non-identifying study IDs and all case report forms and samples are labeled with this information. The code for these IDs is stored in locked files in the locked office of the project manager. Only approved VA research employees will have access to study samples and data.

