## **Adverse Event Definitions**

Adverse Event (AE): An AE is any undesirable medical event occurring to a subject in a clinical trial, if related to the trial product(s). This includes events reported from the first trial related activity after the subject has signed the informed consent and until post treatment follow-up period as defined in the protocol. The following should not be recorded as AEs, if recorded as medical history/concomitant illness on the CRF at screening:

- Pre-planned procedure, unless the condition for which the procedure was planned has worsened from the first trial related activity after the subject has signed the informed consent
- Pre-existing conditions found because of screening procedures

Clinical Laboratory Adverse Event: A clinical laboratory AE is any clinical laboratory abnormality regarded as clinically significant i.e. an abnormality that suggests a disease and/or organ toxicity and is of a severity, which requires active management, (i.e. change of dose, discontinuation of trial product, more frequent follow-up or diagnostic investigation).

Serious Adverse Event (SAE): A serious AE is an experience that at any dose results in any of the following:

- Death
- A life-threatening\* experience
- In-patient hospitalization or prolongation of existing hospitalization
- A persistent or significant disability/incapacity
- A congenital anomaly/birth defect
- Important medical events that may not result in death, be life-threatening\*, or required hospitalization may be considered an SAE when, based upon appropriate medical judgement, they may jeopardize the subject and may require medical or surgical intervention to prevent one of the outcomes listed in this definition.

Unanticipated (Unexpected) Adverse events: The terms “unanticipated” and “unexpected” refer to an event or problem in VA research that is new or greater than previously known in terms of nature, severity, or frequency, given the procedures described in protocol-related documents and the characteristics of the study population.

Serious unanticipated problems involving risks to subjects or others include:

- (1) Interruptions of subject enrollments or other research activities due to concerns about the safety, rights, or welfare of human research subjects, research staff, or others.

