- (2) Any work-related injury to personnel involved in human research, or any research-related injury to any other person, that requires more than minor medical intervention (i.e., basic first aid), requires extended surveillance of the affected individual(s), or leads to serious complications or death.

Serious Adverse Drug Reaction (SADR): An adverse drug reaction (ADR) is an adverse event for which a causal relationship (Possible/Probable relation) between the study drug and the occurrence of the event is suspected. The ADR should be classified as serious if it meets one or more of the seriousness criteria.

Non-Serious Adverse Event: A non-serious AE is any AE which does not fulfil the definition of an SAE.

Severity Assessment Definitions:

- Mild: Transient symptoms, no interference with the subject’s daily activities
- Moderate: Marked symptoms, moderate interference with the subject’s daily activities
- Severe: Considerable interference with the subject’s daily activities, unacceptable

Related AE or a Related Problem: A “related” AE or a “related” problem in VA research is an AE or problem that may reasonably be regarded as caused by, or probably caused by, the research.

Collection, Recording and Reporting of Adverse Events: All events meeting the definition of an adverse event must be collected and reported from the first trial related activity after the subject has signed the informed consent and until the end of the post-treatment follow-up period as stated in the protocol.

Follow-up of Adverse Events: During and following a subject’s participation in a clinical trial, the sponsor-investigator and institution will provide adequate medical care to the study subject for

any study-related adverse events, including clinically significant laboratory values related to the study as per local VA policy.

All adverse events classified as serious or severe or possibly/probably related to the trial product must be followed until the subject has recovered, is recovering, or the condition has reached a new stable condition, and all queries have been resolved according to local VA policy.

Pregnancy: Study subjects will be instructed to notify the sponsor-investigator immediately if they become pregnant. Pregnancy complications should be recorded as adverse event(s). If the infant has a congenital anomaly/birth defect this must be reported and followed up as a serious adverse event.

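### Glucose events that the protocol calls adverse events can miss both of its adverse-event definitions when judged unrelated to the product

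*Combined protocol and SAP*

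**What the plan says.** Two parts of the protocol bear on this.

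Study Approach, under Diabetes care during the study, groups the glucose events with AEs: "With hypoglycemia, excessive hyperglycemia or other adverse events - we will work with the participant and/or primary care team". The response it describes is to "evaluate/change contributory diet or behavior and/or reduce/modify other diabetes medications as appropriate". The same paragraph discourages adding diabetes agents but allows it where clinically indicated.

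Adverse Event Definitions gives two routes by which a non-serious event can become an AE:

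- **General definition.** "An AE is any undesirable medical event occurring to a subject in a clinical trial, if related to the trial product(s"). It sets no condition on how the event is managed.
- **Clinical laboratory AE.** This is "any clinical laboratory abnormality regarded as clinically significant i.e. an abnormality that suggests a disease and/or organ toxicity", and the abnormality must also be one that "is of a severity, which requires active management, (i.e. change of dose, discontinuation of trial product, more frequent follow-up or diagnostic investigation".

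The collection rule in the same section follows from these definitions: "All events meeting the definition of an adverse event must be collected and reported". Separately, Study Visits Schedule provides for routine capture: "At each visit a comprehensive assessment of side effects, medication compliance/competency and concurrent medical history will be obtained and entered into the database".

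**The concern.** Lysulin is given to lower glucose and is added to diet, oral agents or insulin. Hypoglycemia is therefore a natural safety question, and excessive hyperglycemia is a natural sign that treatment is not working. The Background lists hypoglycemia among the side effects of intensified treatment. It also suggests that adding Lysulin could allow less diabetes medication and so fewer side effects.

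Testing that suggestion, or simply describing safety, needs glucose events to be counted in the same way in both arms. If one paragraph calls them AEs and the definitions leave some of them out, the count depends on which paragraph the site follows and on how it judges relatedness. With 60 patients randomized 1:1, or 30 per arm, a few events classified differently could change how the comparison reads. The Statistical Analysis Plan does not settle the matter: it names glucose, HbA1c, AGEs and C-peptide as modeled endpoints and describes no comparison of AEs.

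**Working it through.** The protocol gives no figure to reproduce, and no arithmetic applies. The check is to take a non-serious glucose event of the kind described under Diabetes care and follow it through both definitions.

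**Step 1: the laboratory route, first condition.** The abnormality must suggest disease or organ toxicity. All participants already have type 2 diabetes with HbA1c of at least 7.5%, so a high glucose need not suggest any new disease. A low glucose in a patient on insulin need not suggest disease or organ damage. Glucose fits this condition poorly.

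**Step 2: the laboratory route, second condition.** The list is introduced by i.e., not e.g., so it reads as complete. Its four items are a dose change, stopping the trial product, closer follow-up and further work-up. The responses under Diabetes care compare with it as follows:

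- A change of diet or behavior is not listed.
- An added diabetes agent is not listed.
- A changed dose of another diabetes drug is unclear. The dose item names no drug; only the stopping item is tied to the trial product.
- Evaluation of the event could count as work-up or closer follow-up.

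**Step 3: the general route.** There is no management condition here, so the gaps in Step 2 do not matter. The event must, however, be related to the trial product. Excessive hyperglycemia is hard to attribute to a product meant to lower glucose. Hypoglycemia in a patient on insulin or oral agents is easily attributed to those drugs. The events named under Diabetes care are thus among those that a site could readily judge unrelated.

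**Step 4: both routes together.** The text does not say whether a laboratory AE must also be product-related. The table takes the reading kinder to the plan, that it need not be, and assumes that the action shown was the only one taken.

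| Action taken | Judged related | Judged unrelated |
|---|---|---|
| Product dose changed or product stopped, closer follow-up, or work-up | AE (general) | Laboratory AE, if Step 1 is met |
| Dose of another diabetes drug changed | AE (general) | Depends on how the dose item is read, and on Step 1 |
| Diet or behavior changed, or an agent added | AE (general) | Neither definition is met |

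The bottom right cell is the clear gap. The cell above it is ambiguous. A hypoglycemic episode recognized by symptoms, with no laboratory value, never reaches the laboratory route and rests on Step 3 alone.

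**The case against.** The strongest reply is that failing the laboratory definition is not the same as going unrecorded. A product-related glucose event handled by diet or by changing insulin meets the general definition and must be collected. Side effects and concurrent history go into the database at every visit, and medication changes are monitored in all subjects. Diabetes care itself calls these events adverse, which tells staff how to regard them. The subsections on adverse drug reactions, related AEs and follow-up treat relatedness as something judged about an AE, which suggests that unrelated events were also meant to be recorded. The SAE definition, on its own wording, has no relatedness condition, so a glucose event leading to hospitalization would probably be caught there.

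Most of this stands, and it rules out two stronger readings that a reader might infer:

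- **That the laboratory list covers only actions on the trial product or more monitoring.** The dose item names no drug, so reducing another diabetes drug may fit it.
- **That glucose events handled as Diabetes care describes need not be recorded at all, so the arms cannot be compared on them.** The general definition catches the related ones, and the visit assessments may capture others in some form.

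What the reply does not remove is the non-serious event judged unrelated and handled by diet or an added agent. An entry as a side effect or a medication change is not stated to be an AE record, and no passage defines hypoglycemia or says that glucose events will be tabulated. If the intent was to record AEs whatever their relation to the product, the general definition does not say so.

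**Conclusion.** The point holds in a limited form. Diabetes care during the study and Adverse Event Definitions are not aligned, and one class of glucose event called adverse in the former can meet neither definition in the latter. More of the gap comes from the relatedness condition in the general definition than from the laboratory list, because that condition closes the route that would otherwise catch these events.

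The size cannot be estimated from the documents, which give no rate of glucose events, of actions taken or of relatedness judgments. A reader might assume that 10% to 30% of patients have an excursion acted on through diet or other diabetes drugs, and infer a loss of 3 to 9 of 30 per arm (0.10 × 30 = 3; 0.30 × 30 = 9). The documents do not support that. The rate is assumed, and the figure counts every event acted on, including those that the general definition catches. An imbalance between arms is possible but equally undocumented.

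The conclusion rests on reading the i.e. list as complete and the relatedness condition as it is written. It does not touch the efficacy analysis. Severity is low; this is a cheap improvement.

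**What to change.** Reconcile the two sections with two changes of wording:

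1. In the laboratory AE definition, extend the active-management list to include starting, stopping or changing any other treatment, including diet or other diabetes medication.
2. Add a sentence that hypoglycemia and excessive hyperglycemia acted on under Diabetes care during the study are recorded as AEs whatever their judged relation to the product, and are tabulated by arm.

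The second change does most of the work. The first alone would leave the disease-or-toxicity condition in place and would not reach episodes without a laboratory value. Relatedness can still be recorded for each event, so related and unrelated events can be shown separately.

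Both changes concern recording only and leave clinical management as it is. The cost is protocol and case report form wording. Side effects are already assessed at each visit and medication changes already monitored, so little new information has to be sought. The downside is a somewhat larger reported AE count, including events that have nothing to do with Lysulin.
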